8.1 PRIMARY ANALYSES

The primary outcome for this aim is satisfaction with the intervention. We will calculate descriptive statistics for all variables at baseline and follow-up. Initial analyses will compare binary outcomes between groups using a chi-square test and comparing continuous outcomes (i.e. satisfaction scores) using two sample t-tests. Because ACT intervention is delivered in the form of group sessions, individuals within the same groups will be correlated. All analyses will use the intention-to-treat approach and analyze participants according to randomized group, accounting for intra-group correlation.

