SCRIPT aims to evaluate: 1) the feasibility of ACT with a HIV-positive PWID population in Russia via measures of satisfaction with the intervention, general participation in intervention sessions, and fidelity to the intervention; 2) the impact of ACT on the reduction of HIV and substance use stigma scores, entry into HIV care, substance use frequency, and mental health.

The study's goal is to examine the feasibility of a new intervention and to compare this intervention's effectiveness of reducing internalized stigma with the current standard of care provided by civil society organizations (CSOs) in Russia.

SCRIPT proposes to study a stigma intervention specifically among HIV-positive PWID, broadening its scope to not only HIV-related, but also substance use-related stigma in this key population. By measuring the intervention's effect size on stigma variables and related behavioral outcomes in this population, we will better understand how to intervene on the phenomenon of stigma and ultimately inform the dissemination of stigma interventions in similar health care contexts.

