2.3 STUDY OUTCOMES

Aim 1. The primary outcome for aim 1 is satisfaction with the intervention at month 1, assessed by a satisfaction scale. Secondary outcomes are participation in intervention sessions and fidelity to the intervention, assessed via audio-recording. This will be scored with an ACT Adherence Checklist and the Adherence Raters' Manual for Stigma Treatment Study (Kohlenberg et al, 2004) to rate the recorded intervention audio recordings.

[figure not shown]
Aim 2. The primary outcome for aim 2 is measured change in internalized HIV stigma and substance use stigma at 1 and 6 months assessed by the Berger HIV Stigma Scale, the Leickness HIV internalized shame scale, the modified Substance Abuse Self-Stigma Scale, and the Acceptance and Action Questionnaire – Substance Abuse. Secondary outcomes are initiation of ART, recent (last 30 days) injection drug use frequency at 1 and 6 months, and mental health as measured by the PHQ-9 and GAD-7.

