3. INTERVENTION

3.1 INTERVENTION OVERVIEW

The study will randomize 100 PWID living with HIV in the St. Petersburg area. We will approach potential participants at CSOs serving PWID and people living with HIV (PLWH). After a phone-screening, potential participants will be given clear transportation instructions to the location of the remainder of the procedures (in-person screening, consent, enrollment, assessments, intervention sessions). After in-person screening, consent, enrollment, and the baseline assessment, participants will be randomly assigned to either the SCRIPT intervention or standard of care. Following randomization, participants in both groups will receive standard of care at the study site.

Following randomization by RAs at the rehabilitation center, participants in the intervention group will be scheduled to engage in group ACT sessions. These will consist of three 2-hour group sessions of culturally adapted ACT to reduce stigma and related manifestations in weeks 1, 2 and 3. The ACT sessions are described in further detail in 3.3.A.

Throughout the course of the study, participants will be expected to participate in three in-person assessments (baseline, 1 month [4 weeks], and 6 months [24 weeks]). Participants in the intervention groups will receive three ACT sessions over one month in approximately 13 groups of 5 people each (n=65), with a final assessment conducted at 6 months.

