3.6 DATA SOURCES

3.6.A QUESTIONNAIRES

Questionnaires will be administered at baseline, 1-, and 6-month study visits to collect information about participant demographics (e.g., age, gender), stigma scores, sex risks, substance use risk behaviors, care utilization, general and mental health.

3.6.B SESSION AUDIO RECORDINGS

We will audio-record all intervention sessions and will code a subset of these recordings for quality assurance and fidelity monitoring, i.e., to document adherence to the intervention study procedures.

3.6.C INTERVENTIONIST ADHERENCE CHECKLIST

Interventionists will fill out an intervention adherence checklist to document the items of the intervention that were covered (i.e. specific metaphors, emphasis on homework, etc.)

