8. STATISTICAL ANALYSIS

This study will use an intent-to-treat analysis that includes all participants according to their randomized assignment. Descriptive statistics will be calculated for variables at baseline and each follow-up time to assess whether there appear to be any differences across treatment arms.

Our Specific Aims are to compare the effects of SCRIPT and standard of care on following outcomes:

Aim 1: Evaluate the feasibility of an ACT stigma intervention compared to standard of care via a 2-armed RCT of 100 HIV-positive Russian PWID on the following outcomes:

- Primary: Satisfaction with the intervention at 1 month
- Secondary:
 - Participation in three intervention sessions;
 - Fidelity to the intervention, using the Adherence Raters' Manual for Stigma Treatment Study (Kohlenberg et al, 2004) and an intervention adherence score

Aim 2: Measure changes in internalized stigma

Primary:

- a. HIV Stigma via the Simbayi HIV internalized shame scale at 1 month;
- b. Substance Use Stigma via Modified Substance Abuse Self-Stigma Scale at 1 month

Secondary:

- a. Any initiation of HIV care (ART) at 6 months
- b. Engagement in substance use care at 6 months
- c. Change in last 30 days injection drug use at 6 months

Exploratory:

- a. Depression as measured by the PHQ-9 at 6 months
- b. Anxiety as measured by the GAD-7 at 6 months
- c. Intersectional stigma as measured by both substance use stigma and HIV stigma scales at 6 months
- d. Psychological flexibility measured via the Acceptance and Action Questionnaire at 6 months

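### The Aim 2 primary stigma scores have no stated baseline adjustment; adding it would sharpen the arm comparison at almost no cost

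*Combined protocol and SAP*

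**What the plan says.** Section 8.1 is the whole analysis specification. For continuous outcomes it says: "Initial analyses will compare binary outcomes between groups using a chi-square test and comparing continuous outcomes (i.e. satisfaction scores) using two sample t-tests". No other test or model is named, for Aim 1 or Aim 2. It then adds: "All analyses will use the intention-to-treat approach and analyze participants according to randomized group, accounting for intra-group correlation". It gives no model, variance estimator, degrees-of-freedom method or ICC, and does not say how the ungrouped control arm is handled.

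In sections 8 and 8.1, baseline values have a stated use only under descriptive statistics: "Descriptive statistics will be calculated for variables at baseline and each follow-up time to assess whether there appear to be any differences". No covariate adjustment is mentioned.

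The baseline scores will exist. Section 3.6.A says: "Questionnaires will be administered at baseline, 1-, and 6-month study visits to collect information about participant demographics (e.g., age, gender), stigma scores". The table in section 5.2 lists HIV stigma and substance use stigma at baseline, 1 month and 6 months.

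The form of the outcome varies. Sections 2.1 and 8 list the Aim 2 primary outcomes as scores at one time, for example "Substance Use Stigma via Modified Substance Abuse Self-Stigma Scale at 1 month", under an Aim 2 title that speaks of changes. Section 2.3 says: "The primary outcome for aim 2 is measured change in internalized HIV stigma and substance use stigma at 1 and 6 months".

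**The concern.** At least three analyses of the Aim 2 primary stigma scores fit this text: the 1-month score compared as it stands, the change from baseline, or the 1-month score adjusted for baseline. All three are unbiased under randomisation, but they differ in precision, and the plan does not choose.

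Precision matters here even though the trial is a feasibility study. Section 1.1 says that it will measure the intervention's "effect size on stigma variables and related behavioral outcomes in this population", and it has only 100 participants to do so. Ignoring a baseline score that predicts the outcome widens the interval. A simple change score is worse still than ignoring baseline when the baseline correlation is below 0.5.

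**Working it through.** **Inputs from the document.** 65 ACT and 35 control (section 2.4); about 13 ACT groups of 5 (sections 2.4 and 3.1), so 13 × 5 = 65; controls not grouped. There is no power calculation to reproduce: alpha, power, target effect, SD, dropout, ICC and r are not stated.

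**Assumptions.** Two-sided 5%, 80% power (multiplier 1.960 + 0.842 = 2.802), SD 1 at both times, no loss, the same r in both arms, and baseline explaining no between-group variance (section 4.5 has groups fill after randomisation). ICC is taken from 0.05 to 0.20 and r from 0.3 to 0.7. All of these are illustrative.

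**Formula.** With m = 5 per group, the variance of the arm difference is V = (a + (m − 1) × ICC)/65 + a/35, and the detectable difference is 2.802 × √V. Here a = 1 for the unadjusted score, a = 1 − r² for the baseline-adjusted score and a = 2(1 − r) for the change score.

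**At ICC 0.10:**

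- Unadjusted: V = 1.4/65 + 1/35 = 0.0501, giving 0.627 SD.
- Adjusted, r = 0.5: V = 1.15/65 + 0.75/35 = 0.0391, giving 0.554 SD. Variance ratio to unadjusted: 0.78.
- Change score, r = 0.3: V = 1.8/65 + 1.4/35 = 0.0677, giving 0.729 SD.

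| Analysis (ICC 0.10) | r = 0.3 | r = 0.5 | r = 0.7 |
|---|---|---|---|
| Unadjusted, SD | 0.627 | 0.627 | 0.627 |
| Change score, SD | 0.729 | 0.627 | 0.505 |
| Adjusted, SD | 0.602 | 0.554 | 0.474 |
| Power for 0.5 SD, unadjusted | 61% | 61% | 61% |
| Power for 0.5 SD, adjusted | 64% | 72% | 84% |

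**Range over ICC 0.05 to 0.20.** Unadjusted 0.61 to 0.67 SD. Adjusted 0.58 to 0.64 SD at r = 0.3, 0.53 to 0.60 SD at r = 0.5 and 0.45 to 0.52 SD at r = 0.7.

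**Assumed 20% loss** (52:28, 4 per group, ICC 0.10). Unadjusted 0.69 SD; adjusted 0.66, 0.61 or 0.52 SD.

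**Two effects kept apart.** A naive t-test that ignores the groups assumes V = 1/65 + 1/35 = 0.0440, or 0.587 SD. Accounting for ICC 0.10 raises this to 0.627 SD. So the covariate supplies all of the precision gain, and the grouping term costs precision. Together they come out slightly wider than the naive figure at r = 0.3 with ICC 0.10 (0.60 SD) or 0.20 (0.64 SD), and at r = 0.5 with ICC 0.20 (0.60 SD).

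**Unequal r.** With one common slope and r = 0.5 in ACT but 0.1 in control, the pooled slope is about 0.65 × 0.5 + 0.35 × 0.1 = 0.36. The residual variances are 1 − 2(0.36)(0.5) + 0.36² = 0.770 and 1 − 2(0.36)(0.1) + 0.36² = 1.058. At ICC 0.10, V = (0.770 + 0.4)/65 + 1.058/35 = 0.0482. The variance ratio is then 0.96 rather than 0.78, and most of the gain is gone.

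**The case against.** The strongest reply is that the quoted sentence is worded around satisfaction, an Aim 1 outcome. The table in section 5.2 shows satisfaction collected in the intervention group only, with no baseline, so neither baseline adjustment nor a between-arm t-test applies to it. Read strictly, section 8.1 names no test for the stigma scores at all. That is correct. The point is therefore that the stigma analysis is unspecified beyond those initial t-tests, not that an unadjusted t-test has been fixed for it.

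A reader might also infer that baseline has been confined to description. The change wording in sections 2.1, 2.3 and 8 does not support that, because baseline may be meant to enter through a change score. The loss of precision is measured against two analyses that the text allows, not against one that it mandates.

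The gain also rests on an unknown r. At r = 0.3 it is only 0.63 to 0.60 SD. Equal r in the two arms is an assumption too: section 3.5.A times the 1-month visit from the first group session in ACT and from baseline in control. These limits stand. Within the range checked with equal r, the adjusted analysis was still more precise than either alternative at the same ICC.

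Finally, this is a pilot whose first aim is feasibility, and no bias is involved. That limits the weight of the point but does not remove it, since the change is nearly free.

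**Conclusion.** The point holds as a cheap improvement to the analysis of the two Aim 2 primary stigma scores. Under the assumptions above, with ICC 0.10, adjustment cuts the variance of the arm difference by 8%, 22% or 43% at r = 0.3, 0.5 or 0.7. The gain is smaller if r is lower in the control arm.

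A tempting stronger reading is that the plan ignores grouping and so inflates the error rate. A plain t-test would indeed have a type I error of about 5.8%, 6.6% or 8.3% at ICC 0.05, 0.10 or 0.20. Those figures do not describe this plan, because section 8.1 commits all analyses to accounting for intra-group correlation. What is missing is the method. Naming it delivers that commitment and keeps the error rate valid, at the cost of the slightly wider interval shown above.

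**What to change.** State in section 8.1 that the primary analysis of each Aim 2 primary stigma score is a regression of the 1-month score on arm and baseline score. Once baseline is in the model, using the score or the change as the outcome gives the same arm difference, so that ambiguity is settled.

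Carry out the promised intra-group adjustment inside the model. One suitable form has:

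- a random group intercept in the ACT arm only, with controls as singletons;
- arm-specific residual variance;
- Satterthwaite or Kenward-Roger degrees of freedom, since there are only about 13 groups.

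Define group as the ACT group actually attended, because the missed-visits rule (numbered 3.6.B, under section 4.6) moves anyone who misses session 1 to a later group. Treat never-attenders as singletons and keep everyone in the randomised arm. State how missing 1-month scores are handled. Unadjusted t-tests on the stigma scores can stay as descriptive.

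Limits of the change: it does not apply to satisfaction or to the binary secondary outcomes, and should not be extended automatically to 30-day injection use. The four instruments at 1 and 6 months in section 2.3 and the two at 1 month in section 8 need separate reconciliation.

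Cost: SAP wording, a few lines of code and a record of the group attended. Small-sample degrees of freedom (about 41 to 44 without loss) add about 0.01 to 0.02 SD to the detectable differences above.

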2.4 STUDY DESIGN

SCRIPT is a Randomized Controlled Trial (RCT) among 100 HIV+ PWID, which aims to test the feasibility of the SCRIPT intervention and evaluate its effectiveness on the reduction of internalized stigma as well as self-reported entry into substance abuse treatment or initiation of ART. Eligible participants will be randomly assigned into one of two groups: 1) Control group receiving CSO site standard of care or; 2) ACT intervention. Both the intervention group and the control group will receive standard of care counseling and referral to addiction treatment and HIV treatment at the CSO sites. Following their baseline assessment, participants assigned to the intervention group will meet with the interventionist three times over one month in approximately 13 groups of 5 people each. All three sessions will be in groups, except for the occasional individual make-up 2nd session (more details in section 3.6B). Study outcomes will be assessed at 1 and 6 months (Figure 1).

Figure 1 illustrates the design of this 2-arm RCT with 65 participants in the SCRIPT intervention arm and 35 participants in the standard of care arm.

Figure: SCRIPT Study Design

Throughout the course of the study, participants in both groups will be expected to participate in three in-person assessments (baseline, 1 month and 6 months).

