3.2 RANDOMIZATION

Randomization is not stratified by any factor. Blocked randomization with randomly selected block sizes was used to reduce selection bias and make the sequence less predictable. We generated a random sequence of 34 blocks, sizes 3 and 6. Then, we randomized assignments within each block with an allocation ratio of 2:1. A greater number of blocks was created than is necessary in the event that the investigator continues enrollment beyond the initially planned sample size. Randomization sequence was created in R, version 3.5.2 (Copyright (C) 2018 The R Foundation for Statistical Computing) and uploaded to REDCap platform, electronic data collection tool.

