3.5 SCHEDULE OF DATA COLLECTION

		Phone Screener	Screener and Baseline		ACT Sessions 1-3	1-month assessment (4 weeks)	6 month visit (24 weeks)
			In-person Screener	Baseline			
Screening	Verification of HIV and hx of IDU	X	X				
	Screening Questions	X	X				
Enrollment	Sign Informed Consent		X				
	Complete contact information/verify numbers			X			
Assessment	Baseline Study Assessment			X			
	1-Month Study Assessment incl ACT satisfaction questions					X	
	6-Month Study Assessment						X
	Interventionist Checklist				X		
Randomization	Randomization			X			
Intervention	Adverse Events			X		X	
	ACT Intervention				X		
Other	Compensate for Participation			X	X	X	X
	Provide Resource Card			X			
	Report Adverse Events			X	X	X	X
	Complete Tracking Forms		X	X	X	X	X

Control Group						
		Phone Screener	Screener and Baseline Visit		1 mo (4 weeks)	6 mo (24 weeks)
			In-person Screener	Baseline		
Screening	Verification of HIV and substance use	X	X			
	Screening Questions	X	X			
Enrollment	Sign Informed Consent		X			
	Complete contact information/verify numbers			X		
Assessment	Baseline Study Assessment				X	
	1-Month Study Assessment					X
	6-Month Study Assessment					X
	Randomization				X	
Other	Provide Resource Card				X	
	Compensate for Participation				X	X

	Complete Tracking Forms			X	X	X
--	-------------------------	--	--	---	---	---

3.5.A. VISIT WINDOWS

ACT Intervention Session Windows for Intervention Group

1st ACT Session

- Window open: 1 day post baseline
- Target date: 7 days post baseline
- Window close: 31 days post baseline
- Window length: 30 days

2nd ACT Session

- Window open: 8 days post baseline
- Target date: 14 days post baseline
- Window close: 29 days post baseline
- Window length: 21 days

3rd ACT Session:

- Window open: 15 days post baseline
- Target date: 21 days post baseline
- Window close: 36 days post baseline
- Window length: 21 days

Research Assessment Windows for Intervention and Control Group

Intervention Group 1 Month (4-week) Visit

- Window open: 16 days post first group session
- Target date: 30 days post first group session
- Window close: 90 days post first group session
- Window length: 74 days

Intervention Group 6 Month (24-week) Visit

- Window open: 151 days post first group session
- Target date: 180 days post first group session
- Window close: 240 days post first group session
- Window length: 89 days

Control Group 1 Month (4-week) Visit

- Window open: 16 days post baseline

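### Intent-to-treat analysis of everyone randomised is promised, but only single-visit tests are named and no method is given for missing outcomes

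*Combined protocol and SAP*

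**What the plan says.** Section 8 opens with the commitment: "This study will use an intent-to-treat analysis that includes all participants according to their randomized assignment". Section 8.1 repeats it and adds clustering: "All analyses will use the intention-to-treat approach and analyze participants according to randomized group, accounting for intra-group correlation".

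The only tests named are in 8.1: "Initial analyses will compare binary outcomes between groups using a chi-square test and comparing continuous outcomes (i.e. satisfaction scores) using two sample t-tests".

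The Aim 2 outcomes in Section 8 are each tied to one visit. Both primary stigma scales are at 1 month (for example "HIV Stigma via the Simbayi HIV internalized shame scale at 1 month"). The secondary outcomes are at 6 months (for example "Any initiation of HIV care (ART) at 6 months").

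Neither Section 8 nor 8.1 names an imputation method, a longitudinal model, a rule for a missing outcome, a sensitivity analysis or a separate analysis set. Missing data are mentioned only in 7.2, as a form-coding matter. Yet missing outcomes are foreseen: refused sections are accepted (4.6), no-shows are to be rescheduled (4.8), loss to follow-up is named (6.2, SAE reporting), and an incarceration form is planned (7.3).

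**The concern.** A two-sample t-test on a 1-month score, or a chi-square test on 6-month ART initiation, uses only participants with that value. Adjusting it for group clustering changes the standard error, not who is in the analysis. Once any outcome is missing, the promise to include everyone cannot be kept by the named methods, and a comparison of observed cases would be reported as intent-to-treat.

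Such a comparison is unbiased only if, within each arm, missingness is unrelated to the outcome, or if the resulting errors cancel between arms. The design gives reason not to take this for granted. ACT follow-up is timed from the first group session ("Target date: 30 days post first group session"), control follow-up from baseline. Section 3.5.A gives no anchor for an ACT participant who never attends a first session.

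The stigma scales are collected at baseline, 1 and 6 months (5.2). Scores that could weaken the missing-data assumption and improve precision are therefore available at no extra burden.

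**Working it through.** **Inputs from the documents.** 2.4 plans 100 participants, "with 65 participants in the SCRIPT intervention arm and 35 participants in the standard of care arm". 3.2 gives the ratio: "Then, we randomized assignments within each block with an allocation ratio of 2:1". These agree within 2 participants: 13 groups x 5 = 65, and 2:1 of 100 is 66.7/33.3. The documents state no alpha, power, SD, effect size or dropout rate, so there is no planned figure to reproduce. Everything below is illustration under stated assumptions, without group clustering.

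**Step 1: how many are analysed.** Assume equal loss d in both arms, two-sided alpha 0.05 and 80% power. Then n1 = 65(1-d), n0 = 35(1-d), and the detectable difference is (1.960 + 0.842) x sqrt(1/n1 + 1/n0). At d = 0 this is 2.802 x sqrt(1/65 + 1/35) = 0.59 SD.

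| Loss | Analysed | Detectable (SD) | Power for 0.5 SD |
|---|---|---|---|
| 0% | 100 | 0.59 | 66.5% |
| 10% | 90 | 0.62 | 61.9% |
| 20% | 80 | 0.66 | 56.9% |
| 30% | 70 | 0.70 | 51.4% |

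**Step 2: unequal loss is what biases.** If dropouts score 0.5 SD worse than completers in both arms, equal loss gives zero bias. Loss of 10% versus 30% gives 0.5 x (0.30 - 0.10) = 0.10 SD, with the sign set by which arm loses more.

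**Step 3: ACT loss depends on baseline stigma.** Assume no treatment effect, standard-normal scores, baseline to 1-month correlation r = 0.4-0.6, and control loss of 15% at random. ACT loss is L = 15-35%, with log-odds rising by s = 0.5-1.0 per SD of baseline. Negative means lower stigma in ACT. Let D be the mean baseline of observed ACT participants: D = E[x(1 - p(x))]/(1 - L), where p(x) is the logistic loss probability. Numerical integration gives D = -0.073 (L = 15%, s = 0.5) to -0.292 (L = 35%, s = 1.0).

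- t-test on the 1-month score: bias = rD, from 0.4 x (-0.073) = -0.03 to 0.6 x (-0.292) = -0.18. Simulations at 65:35 and 67:33 give about -0.03 to -0.19.
- t-test on change: bias = (r - 1)D, from (-0.4) x (-0.073) = +0.03 to (-0.6) x (-0.292) = +0.18. Simulated: about +0.02 to +0.18.
- Baseline-adjusted: bias is zero in theory and within about 0.01 in simulation. This is built in, because loss was made to depend on baseline alone.

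**Step 4: ACT loss depends on the 1-month score.** With the same rates and slopes, observed ACT participants have mean D at 1 month and rD at baseline.

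- 1-month score: D, or -0.07 to -0.29 (simulated to -0.30).
- Change: (1 - r)D, from 0.4 x (-0.073) = -0.03 to 0.6 x (-0.292) = -0.18, now towards ACT.
- Baseline-adjusted: about (1 - r^2)D, from 0.64 x (-0.073) = -0.05 to 0.84 x (-0.292) = -0.25, as simulated.

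**Step 5: precision.** The simulated SE is about 0.22-0.25 SD unadjusted and 0.18-0.23 SD baseline-adjusted. This fits the usual factor sqrt(1 - r^2), which is 0.92 at r = 0.4 and 0.80 at r = 0.6: 0.25 x 0.92 = 0.23 and 0.22 x 0.80 = 0.18.

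**The case against.** **The tests are only a first step.** 8.1 labels them initial, its continuous example is satisfaction, and all analyses must account for clustering, so a further unnamed model is implied. No sentence assigns a t-test to the stigma scales explicitly. This stands against calling the plan wrong as written. It does not close the gap: no later model is named, and a cluster-adjusted single-visit model still omits missing outcomes. Satisfaction is collected only in the ACT arm (5.2, a separate problem), so a between-group test of continuous outcomes can in practice only concern measures such as the stigma scales.

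**Analysing as randomised is intent-to-treat.** The named tests can meet that half. The half they cannot meet is including everyone.

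**Baseline may be used after all.** Aim 2 speaks of measuring changes, and 2.3 defines its primary outcome as change. A change-score t-test is a natural reading. This stands, and it reverses the direction of bias in Step 3.

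**Higher ACT loss is not documented.** ACT participants are paid for each session (4.7) and have more contact. Those who miss session 1 are moved to the next group, and those who miss session 2 or 3 are still scheduled or invited for both assessments (4.6, missed visits). Window lengths are the same in both arms, at 74 and 89 days (3.5.A). Phone assessment is a last resort (4.7, 5.2) and tracing is extensive (4.8). This stands: which arm would lose more is unknown.

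**It is a small feasibility trial.** True, so the remedy should be modest. But 1.1 also sets out to compare effectiveness on internalised stigma, and Section 8 names two primary stigma outcomes.

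**Conclusion.** The concern holds as a mismatch between the promised population and the named methods, with no missing-outcome method to bridge it. It matters only to the extent that outcomes are missing, which the documents foresee but do not quantify.

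A reader might infer that following the plan would favour ACT. The documents do not support that. The sign depends on whether the score or its change is tested, on which arm loses more, and on what drives the loss. The ranges of -0.03 to -0.19 SD and +0.02 to +0.18 SD rest on assumed loss rates, slopes, correlations and a mechanism confined to the ACT arm.

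A reader might also infer that baseline adjustment removes the bias. It does so only if loss depends on baseline alone. If loss depends on the 1-month score, about -0.05 to -0.25 SD remains. What baseline adjustment does deliver is a lower SE (about 0.18-0.23 versus 0.22-0.25 SD) and a weaker assumption, missing at random. This is a worthwhile, inexpensive improvement rather than a fatal flaw.

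**What to change.** For the two stigma scales, replace the t-test with a likelihood-based repeated-measures model of the baseline, 1-month and 6-month scores, with arm-by-visit terms. Enter baseline as a response, constrained equal across arms, and allow for group clustering in the ACT arm. Every randomised participant with a baseline then enters the model. Those with a baseline only add little directly to the effect estimate; the gain comes mainly from conditioning on baseline and from the 6-month scores. With baseline so constrained, the arm difference at 1 month equals the arm difference in change, which also settles the score-or-change ambiguity.

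At minimum, use ANCOVA adjusting for baseline, described as an analysis of observed outcomes. With baseline only as a covariate, a participant without follow-up drops out, so ANCOVA does not include everyone.

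Add one missing-not-at-random (delta) sensitivity analysis for the stigma scales and, for ART initiation, one that counts missing as not initiated. State the analysis set and missing-data assumption for each outcome, and describe any complete-case result as such.

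Cost: SAP wording and some programming, no new data collection, and slightly more complex analysis and reporting.

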3.3 INTERVENTION

The SCRIPT intervention is comprised of a culturally adapted ACT intervention designed to reduce stigma and related manifestations. Both ACT and standard of care groups will receive the usual care at the CSO and study sites, which includes counseling and referral to addiction treatment clinics (for detox and rehabilitation; opioid agonist treatment is not available in Russia) and to HIV treatment clinics (for ART and HIV care) in St. Petersburg (standard of care).

3.3.A. ACCEPTANCE AND COMMITMENT THERAPY (ACT)

The ACT intervention will consist of three sessions scheduled for 2 hours each. Sessions will occur in groups of approximately 5 and will follow an intervention manual, based on the one developed in Luoma et al. (2008) and Luoma et al. (2012) and culturally adapted to a Russian context by the study team. Participants are told that the groups are intended to help them overcome stigmatization, shame and judgments of self and others. Standard ACT exercises are modified to focus on how to respond to shame and self-stigmatizing thoughts in a

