3.4 CONTROL GROUP

Participants in the control group will receive standard care as normally provided to patients by civil society organizations. This could include information on HIV and substance use disorders, counseling, referral to addiction treatment clinics, and referral to HIV treatment clinics. They might also be given printed information, including phone numbers, on places that provide HIV medical care and substance use treatment.

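### Session participation and fidelity fall under between-arm tests, but controls have no sessions, so the comparison says almost nothing about feasibility

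*Combined protocol and SAP*

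**What the plan says.** Section 8 introduces the aims with "Our Specific Aims are to compare the effects of SCRIPT and standard of care on following outcomes". Aim 1, in sections 2.1 and 8, is framed as a comparison with standard of care. Its secondary outcomes are "Participation in three intervention sessions" and fidelity to the intervention.

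Section 8.1 gives the method: "Initial analyses will compare binary outcomes between groups using a chi-square test", and two-sample t-tests for continuous outcomes, with satisfaction scores as the example. It adds "All analyses will use the intention-to-treat approach and analyze participants according to randomized group, accounting for intra-group correlation". It also promises descriptive statistics for all variables.

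On the control arm, section 3.4 says "Participants in the control group will receive standard care as normally provided to patients by civil society organizations". The control schedule in section 3.5 has no ACT session column. Section 5.2 marks the satisfaction items as collected from intervention participants only.

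The documents do not define participation as binary or as a count. They state no alpha, no ICC and no completion level that would count as feasible.

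**The concern.** A between-arm test is informative when both arms could have had the outcome. Here one arm cannot. The control count of completers is 0 by design, so the test asks whether anyone at all finishes a course that only the other arm can attend. The feasibility question is whether enough of those offered the course finish it. A test against a fixed zero becomes significant at a completion rate far below anything likely to be called feasible, and it gives nearly the same answer at 30% as at 80%.

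Fidelity is worse placed. There are no control sessions to rate, so the comparison is undefined.

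Feasibility is the first aim and half of the central hypothesis, and section 1.1 names satisfaction, participation and fidelity as its measures. Of the three, only participation yields a between-arm test that can actually be computed, and that test is close to guaranteed to be significant.

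**Working it through.** The plan states no power, alpha or feasibility figure, so there is none of its own to reproduce. Its group arithmetic is consistent: 13 groups × 5 = 65.

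**Inputs**
- Arms: "65 participants in the SCRIPT intervention arm and 35 participants in the standard of care arm" (section 2.4). Section 3.2 states "we randomized assignments within each block with an allocation ratio of 2:1", so about 67:33 is a sensitivity case.
- Control completers: 0 of 35, by design (sections 3.4 and 3.5).
- Cluster size: "Sessions will occur in groups of approximately 5" (section 3.3.A).
- Assumed, because not stated: two-sided alpha 0.05; ICC 0 to 0.2; participation coded as all three sessions, yes or no.

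**1. Smallest significant count.** With x completers of 65 against 0 of 35, Pearson chi-square reduces to

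X² = 100 × 35 × x / [65 × (100 − x)], compared with 3.84.

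- x = 6: 21,000 / 6,110 = 3.44, p = 0.064.
- x = 7: 24,500 / 6,045 = 4.05, p = 0.044.

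| Test | 65:35 | 67:33 |
|---|---|---|
| Pearson, uncorrected | 7 (10.8%) | 8 (11.9%) |
| Fisher exact | 8 (12.3%) | 8 (11.9%) |
| Yates-corrected | 10 (15.4%) | 10 (14.9%) |

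**2. Allowing for session groups.** Section 8.1 promises this but names no method. A crude version divides X² by 1 + (5 − 1) × ICC.

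- ICC 0.05: divisor 1.2; x = 8 gives 4.68 / 1.2 = 3.90. Threshold 8 (12.3%).
- ICC 0.10: divisor 1.4; x = 10 gives 5.98 / 1.4 = 4.27 (x = 9 gives 3.80, not enough). Threshold 10 (15.4%).
- ICC 0.20: divisor 1.8; x = 12 gives 7.34 / 1.8 = 4.08. Threshold 12 (18.5%).

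**3. Probability of a significant result.** Binomial with n = 65 when unclustered; beta-binomial with 13 groups of 5 when clustered, each with its own adjusted threshold.

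| Analysis | True completion 20% | True completion 30% |
|---|---|---|
| Pearson, ICC 0, x ≥ 7 | 0.98 | >0.99 |
| Fisher, ICC 0, x ≥ 8 | 0.96 | >0.99 |
| Yates, ICC 0, x ≥ 10 | 0.86 | 0.998 |
| ICC 0.05, x ≥ 8 | 0.95 | >0.99 |
| ICC 0.10, x ≥ 10 | 0.82 | 0.99 |
| ICC 0.20, x ≥ 12 | 0.62 | 0.95 |

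**4. If participation is a session count.** Every control value is 0, so the t-test only asks whether the ACT mean exceeds zero. The fault is the same.

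**5. What a one-arm estimate gives.** For n = 65 the 95% half-width is 1.96 × √[p(1 − p)/65 × (1 + 4 × ICC)]. At 80% completion this is 9.7 points at ICC 0 and 11.5 at ICC 0.10. By exact (Clopper-Pearson) lower bounds before clustering, 41 of 65 clears a 50% floor (bound 50.2%) and 48 of 65 clears a 60% floor (bound 61.5%). The 60% rule would be met with probability about 0.91 at a true 80%, 0.014 at a true 60%, and essentially 0 at a true 20%. Unlike the between-arm test, it separates these cases.

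**The case against.** The strongest reply is that the documents never say that participation is tested by chi-square. Section 8.1 speaks of binary outcomes in general and names only satisfaction. Section 1.1 describes feasibility as evaluated through satisfaction, participation and fidelity with no comparator, and ties the comparison with standard of care to internalized stigma. This stands as a caution: the reading comes from putting sections 8 and 8.1 together. But sections 2.1 and 8 do word Aim 1 as compared with standard of care, and section 8.1 does send another ACT-only measure, satisfaction, to a two-sample test. The drafting gives no exemption, and reading participation as a count does not remove the problem.

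A reader might infer that the plan would declare ACT feasible on a significant p-value even if four in five participants failed to finish. The documents do not support that. Nothing makes feasibility depend on a p-value, and the promised descriptive statistics would show the ACT completion rate. What remains is that no threshold or rule for interpreting that rate is given, so a near-automatic p-value is the only inferential output available for it.

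A reader might also take the 11% threshold, or near-certain significance at 20% completion, as how the planned analysis behaves under strong clustering. It is not. Once the promised allowance for intra-group correlation is applied at ICC 0.2, the threshold is 12 of 65 and the probability at 20% completion is 0.62.

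Finally, the satisfaction conflict is the more explicit one and concerns the primary Aim 1 outcome. That is a reason to repair all three measures in one edit.

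**Conclusion.** The concern holds as a defect of analysis specification. As drafted, participation is compared with a structural zero and fidelity with nothing. Under the assumed two-sided 0.05 and binary coding, significance begins at about 11% to 15% completion without clustering, depending on the form of the test, and at about 12% to 18% with a crude design effect on the uncorrected test at ICC 0.05 to 0.2. At a true completion of 30% the test is significant with probability at least 0.95 in every variant tried at 65:35. It cannot tell whether enough people complete the course.

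The exact figures rest on assumed alpha, coding and ICC; the structural fault does not. The data to be collected are sound, and the outcome is secondary, so this should be corrected but does not threaten the trial. The larger gap behind it is the absence of any criterion for feasible completion.

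**What to change.** In sections 2.1, 8 and 8.1, remove participation and fidelity from the between-arm comparison, together with satisfaction, which section 5.2 collects in the intervention group only. Then:

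- **Participation:** report the proportion of all participants randomised to ACT who complete three sessions, with a 95% CI. Groups form after randomisation (section 4.5), so some participants may never join one. Count those who attend no session as non-completers and treat each as a singleton in any cluster-robust interval.
- **Definition:** state whether the individual make-up second session, described under missed visits, counts towards the three.
- **Criterion:** judge the lower confidence bound against a floor that the sponsor chooses and fixes before outcome data are examined. The 50% and 60% floors above are illustrations only.
- **Fidelity:** report it descriptively in the ACT arm, at session level.
- **Between-arm tests:** keep them for outcomes both arms can have, such as ART initiation and engagement in substance use care.

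The cost is a wording change with no new data. The downside is that the sponsor must commit to a floor, and the feasibility claim can then fail.
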